### 7.1.5 Specific Guidance for Transaminase Elevations

If a participant experiences an ALT level  $\ge 5 \times ULN$  that is  $\ge 2 \times Baseline$ , a confirmatory test must be performed within 72 hours. If the ALT is confirmed  $\ge 5 \times ULN$ , the management guidelines in Table 7-4 must be followed.

If a participant experiences an increase in ALT by one or more toxicity grades compared to the previous nadir (for example, ALT Grade 0 at nadir increases to Grade 1 or above, or ALT Grade 1 at nadir increases to Grade 2 or above), safety laboratory assessments and clinical evaluation of the participant should be conducted within 1 week.

Alternative management of ALT increases requires approval from the A5348 protocol core team by email at [contact].

ALT ≥10 x ULN	Permanently discontinue study drugs. Evaluate and manage the participant as medically appropriate.
ALT > 5 x ULN and >2 x baseline	Evaluate and manage the participant as medically appropriate. Continue study drugs and repeat liver function tests within 3 days and as clinically indicated until resolution. Perform clinical assessment within 1 week. If ALT values during follow-up are increased >2-fold from the prior values, then permanently discontinue study drugs.

Table 7-4: Management of Confirmed ALT Levels  $\geq 5 \times ULN$  and  $\geq 2 \times Baseline$ 

### 7.1.6 HIV-1 Virologic Failure

Plasma HIV-1 RNA will be monitored throughout the study for participants on ARV. In this study, HIV-1 viral failure will be defined as confirmed increase in HIV-1 RNA to  $\geq$ 200 copies/mL at any time after study entry, only for participants who are taking ARV.

Since "blips" in HIV-1 RNA may be observed in individuals on ARV in the absence of HIV-1 VF, any increase in plasma HIV-1 RNA ≥200 copies/mL must be confirmed with repeat testing as soon as possible (not to exceed 2 weeks). For participants with confirmed HIV-1 VF, a plasma specimen obtained at the time of confirmation will be sent to the designated central laboratory for evidence of HIV-1 drug resistance. Confirmed HIV-1 VF specimens must have repeated detection of ≥200 copies/mL for HIV-1 drug resistance testing. Results will be reported back to sites in real-time from the designated central laboratory.

Clinical management of HIV-1 VF will be handled by local site investigators according to current HIV treatment guidelines and local standard of care. The A5348 protocol core team must be contacted to notify of any changes in ARV regimen in the event of HIV-1 VF ([contact]).

Investigators should consult section 5.0 and the package insert.

Regarding the potential for a modified ARV regimen for HIV-1 VF: Possible modified ARV regimens should take into account the unique characteristics of the participant and the participant's HIV treatment history as well as known and/or anticipated drug interactions with DAA or DAA+RBV therapy.

If no reasonable salvage HIV regimens compatible with continued HCV DAA or DAA+RBV therapy are deemed available for an individual participant with HIV-1 VF then the participant must discontinue HCV DAA+RBV therapy.

#### 7.2 Pregnancy

Pregnancy will result in immediate discontinuation of the study medications in both Arm A and Arm B; for those in Arm A assigned to RBV, initiation of counseling regarding the teratogenicity of RBV. Participants who become pregnant while on study will be followed on study/off treatment until study completion. A visit 6 months following the end of pregnancy will be conducted for evidence of AEs in the participant and infant, and an outcome CRF will be completed. For female participants, obstetrical history will also be recorded on the CRF.

Male participants whose partners become pregnant will undergo treatment discontinuation and remain on study for continued follow-up until the end of the study. They will receive counseling on RBV teratogenicity and the same follow-up visit at 6 months after their partners' delivery as outlined for pregnant women.

Participants who become pregnant while taking study treatment or within 6 months after discontinuing study treatment and male participants' sexual partners who become pregnant during this time, will have their pregnancies reported to the RBV Pregnancy Registry (www.RibavirinPregnancyRegistry.com).

If a female participant or female partner of a male participant has completed the study or chooses to discontinue from the study before the end of the pregnancy, then site staff should request permission to contact her regarding pregnancy outcomes at the end of pregnancy. If the information is obtained, pregnancy outcomes will be submitted on a CRF at the end of the pregnancy.

The intrapartum complications and/or pregnancy outcome will be recorded on the CRFs. If applicable, pregnancies that occur on study should be reported by the site investigator prospectively to The Antiretroviral Pregnancy Registry. More information is available at www.apregistry.com. [contact]; [contact].

7.3 HCV Virologic Response-Based Stopping Criteria and Confirmation of VF/Relapse

The following on-treatment HCV virologic response-based treatment stopping criteria will be utilized for all participants:

- Confirmed increase in HCV RNA ≥LLOQ if HCV RNA previously declined to <LLOQ (detected or not detected). This will be defined as HCV breakthrough.
- Confirmed ≥1 log10 IUmL HCV RNA on-treatment increase from nadir.
- Confirmed HCV RNA ≥LLOQ at week 8 visit.

Confirmation will be required for all stopping criteria and should be performed as soon as possible but within 2 weeks after determination of initial observation (see HCV VF Confirmation in section 6.2.4).

HCV RNA measurement to confirm treatment failure or relapse after treatment will be performed in real time at the designated laboratory and the results will be provided to the site investigators within 2 weeks of specimen receipt. If treatment failure is confirmed, then all study treatment should be stopped. However, participants should be followed as per section 6.2.4.

Retreatment of HCV virologic failures will not be provided through A5348.

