#### 6.2.3 Post-Entry Evaluations

# Step 1: On-Treatment Evaluations

On-treatment (Step 1) visits are scheduled in reference to the date of study entry. Weeks 1 and 2 have a window of  $\pm 3$  days. Weeks 4, 8, 12, 16, 20, and 24 have a window of  $\pm 7$  days. Only those participants randomized to Arm B will have weeks 16, 20, and 24 on-treatment evaluations.

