#### 6.2.4 Event Driven Evaluations

## HCV Virologic Failure/Relapse Confirmation

Participants with suspected HCV VF, as defined in section 7.3, must have a confirmation sample obtained as soon as possible, but within 2 weeks of initial notification of HCV RNA meeting criteria for HCV VF. Participants who permanently discontinue study treatment for HCV VF (see details in section 7.3) will be followed on study/off treatment in Step 2 per the SOE.

Virologic evidence of HCV relapse, defined as HCV RNA <LLOQ at end-oftreatment but HCV RNA ≥LLOQ during follow-up, will require confirmation and the sample should be obtained and the sample sent in real time to the designated laboratory as soon as possible but within 2 weeks after determination of initial observation. The results will be provided to the site investigators within 2 weeks of specimen receipt.

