#### HCV RNA (on-study evaluations)

At the entry and post-entry visits, HCV RNA quantification will be performed at the designated testing laboratory) as follows:

Serum HCV RNA real-time testing will be collected, processed, and shipped to the designated testing laboratory (see A5348 laboratory processing chart [LPC] for instructions). These results will be reported within 2-3 weeks after specimen receipt.

NOTE: The study team should be notified ([contact]) of detectable HCV RNA after week 4 of study treatment.

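### Does the week-8 HCV stopping rule come too late to matter in the 12-week arm?

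*Protocol*

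**What the plan says.** Protocol section 7.3 opens its list of three criteria with "The following on-treatment HCV virologic response-based treatment stopping criteria will be utilized for all participants". The third criterion is "Confirmed HCV RNA ≥LLOQ at week 8 visit". Treatment stops only once failure has been confirmed. SAP section 2.3 repeats the three criteria without distinguishing the arms, and SAP section 2.2 makes the length of treatment in each arm depend on HCV response.

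The times come from three places:

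- **First result.** Protocol section 6.3.8, on on-study HCV RNA: "These results will be reported within 2-3 weeks after specimen receipt".
- **Repeat sample.** Protocol section 6.2.4: participants with suspected failure "must have a confirmation sample obtained as soon as possible, but within 2 weeks of initial notification of HCV RNA meeting criteria for HCV VF". SAP section 2.3 sets the same two-week ceiling.
- **Second result.** Protocol section 7.3: "the results will be provided to the site investigators within 2 weeks of specimen receipt", with testing in real time.

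The week-8 visit may fall seven days either side of its target (Protocol section 6.2.3), which SAP section 2.6 writes as days 49 to 63. Arm A participants move to post-treatment follow-up at week 12 and Arm B participants at week 24.

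**The concern.** Adding the three delays to week 8 appears to use up all of Arm A's remaining treatment. A site could keep to every stated limit and still learn of a confirmed failure after the participant had taken the last dose. A rule written for everyone would then shorten treatment in Arm B but have little effect in Arm A.

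Two things would be at stake. Some Arm A participants would stay on LDV/SOF and ribavirin after meeting a criterion meant to stop treatment. Also, the same week-8 virology could be tabulated under SAP section 4.1.5 as completed treatment in Arm A and as stopping for virologic failure in Arm B, so the two columns of that table would not mean quite the same thing.

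**Working it through.** The documents give no date by which the rule should take effect, so there is no stated figure to reproduce. The check is calendar addition:

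day of action = V + T1 + C + T2

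- V, day of the week-8 visit: 56, range 49 to 63 (Protocol 6.2.3, SAP 2.6).
- T1, time to first result: 14 to 21 days if the stated two to three weeks is a range, or 0 to 21 if it is a ceiling (Protocol 6.3.8).
- C, time to repeat sample: 0 to 14 days (Protocol 6.2.4, SAP 2.3).
- T2, time to second result: 0 to 14 days (Protocol 7.3).
- End of treatment: Arm A 12 × 7 = day 84; Arm B 24 × 7 = day 168.

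Shipping time is not stated and is set to 0. Treatment may start up to 48 hours after randomization (Protocol 6.2.2), which can move the last dose about 2 days later.

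| Case | V + T1 + C + T2 | Day | Relative to day 84 |
|---|---|---|---|
| On-time visit, all limits | 56 + 21 + 14 + 14 | 105 | 21 after |
| Same, first result at 2 weeks | 56 + 14 + 14 + 14 | 98 | 14 after |
| 3-week first result, same-day resample | 56 + 21 + 0 + 14 | 91 | 7 after |
| 2-week first result, same-day resample | 56 + 14 + 0 + 14 | 84 | same day |
| Same, second result in 1 week | 56 + 14 + 0 + 7 | 77 | 7 before |
| Early visit, second result at its limit | 49 + 14 + 0 + 14 | 77 | 7 before |
| One week for each step | 56 + 7 + 7 + 7 | 77 | 7 before |
| Late visit, all limits | 63 + 21 + 14 + 14 | 112 | 28 after |

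The row with one week for each step applies only if the first-result time is read as a ceiling. With T1 at 14 to 21 days, an on-time visit gives action anywhere from day 70 (56 + 14 + 0 + 0) to day 105.

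**Arm B.** The latest case is day 112, leaving 168 − 112 = 56 days of treatment. The rule always acts in time there, apart from shipping.

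**Treatment at stake in Arm A.** Counting from day 56 would overstate the loss, because the rule never stops treatment before confirmation. With T1 of at least 14 days, the earliest possible stop is day 70 for an on-time visit and day 63 for a day-49 visit. The most that slow handling can add is 84 − 70 = 14 days, or 84 − 63 = 21 days. If first results came back faster than two weeks, more days could be saved, but the rule would also act before day 84 more easily.

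**The other two criteria.** Breakthrough and a tenfold rise from nadir can be met earlier, since HCV RNA is also measured at weeks 1, 2 and 4. A trigger at an on-time week-4 visit, with every step at its limit, gives 28 + 21 + 14 + 14 = day 77, still before the end of Arm A treatment.

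**The case for a change.** The case for a change is that the documents clearly mean the rule to act during Arm A treatment. Section 7.3 describes the criteria as on-treatment ones, section 8.1 lists HCV failure as a reason for stopping early, and SAP 2.2 ties Arm A's duration to response. A site that meets every deadline can still find that the week-8 rule had no effect. Shipping time only tightens this. With a late visit and a three-week first result, notice arrives on day 63 + 21 = 84, before any repeat sample. SAP 4.1.5 and 4.3.1 do not say how to label an Arm A failure confirmed after the last dose, and comparing tolerability between arms is a secondary objective.

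The arithmetic at the limits stands, and so does the asymmetry between arms. The further steps do not.

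- The passages do not contradict each other. A criterion can apply to everyone and still take effect late for some. Both confirmation steps are to be done quickly, with two weeks as the outer limit.
- HCV RNA is watched outside the formal rule. The study team is to be told of detectable HCV RNA after week 4 (Protocol 6.3.8), and the core team reviews results routinely (Protocol 9.5, SAP 2.7.1).
- SAP 4.1.5 is a descriptive summary with no test between arms. The virology is reported elsewhere: details of each HCV virologic failure in SAP 4.2.5, reasons for non-response in SAP 4.3.1, and every participant's HCV RNA by visit week in SAP 4.4.2. An Arm A participant above the limit of quantification at week 8 would be visible whatever the stated reason for stopping.

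**Conclusion.** No change is needed. At the permitted limits the week-8 rule would take effect in Arm A on day 98 to 105 for an on-time visit, against a last dose at about day 84. With prompt handling or an early visit it can act by day 77. The treatment at stake is at most about 14 days for an on-time visit and 21 for a day-49 visit, assuming a first result no sooner than two weeks and no shipping delay. Requiring confirmation protects against stopping on a single spurious result, and the time it takes weighs more heavily on a short regimen. That is a fair trade-off.

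The primary result is unaffected. SVR12 is estimated separately in each arm and timed from the actual last dose, so it is defined the same way whether or not the rule acted. A failure confirmed after treatment still serves classification and resistance testing. Protocol section 9.1 already says that comparisons between arms are unpowered and need caution. With 7 participants and a final report made up mainly of listings (SAP sections 1 and 2.5.2), an analyst can see from the individual records whether an Arm A completer had met the week-8 criterion and say so beside the table of reasons for stopping.

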### 8.0 CRITERIA FOR DISCONTINUATION

- 8.1 Premature Study Treatment Discontinuation
  - Drug-related toxicity (see section 7.1 Toxicity).
  - Pregnancy in a female participant or in the female partner of male participant.
  - HCV failure as defined in section 7.3.
  - Failure by the participant to attend three or more consecutive clinic visits.
  - Seven or more missed consecutive doses of study treatment.
  - Participant requests to discontinue for any reason.
  - Requirement for prohibited concomitant medications (see section 5.4).
  - Breastfeeding.

• Clinical reasons believed life threatening by the physician, even if not addressed in the toxicity section of the protocol.

## 8.2 Premature Study Discontinuation

- Request by the participant to withdraw.
- Request of the primary care provider if s/he thinks the study is no longer in the best interest of the participant.
- Participant judged by the investigator to be at significant risk of failing to comply with the provisions of the protocol as to cause harm to self or seriously interfere with the validity of the study results.
- At the discretion of the Study Monitoring Committee (SMC), ACTG, institutional review board (IRB), NIAID, Office for Human Research Protections (OHRP), any other government agency as part of their duties, investigator, or industry supporter.
- Initiation of alternate non-study HCV treatment.

### 9.0 STATISTICAL CONSIDERATIONS

#### 9.1 General Design Issues

A5348 is a prospective, open-label study to evaluate 12-week and 24-week regimens of LDV/SOF (Arms A and B, respectively) for the retreatment of HCV among individuals with prior treatment failures, with the addition of RBV to the 12-week regimen. It is a study to gather timely, pilot data in the retreatment of HCV in HIV-coinfected persons and to complement similar studies in HCV mono-infected persons, planned outside of the ACTG. The study will randomize the participants to the study arms, since there is clinical equipoise on the benefits and drawbacks between a shorter 12-week regimen of LDV/SOF with RBV and a 24-week regimen without RBV (see section 2.2 Rationale). The primary analysis will be conducted as a single-arm analysis for each regimen. Any comparison made between the regimens will be done as a secondary analysis. The study has not been designed to be powered for comparison between the two study regimens, and as such, any comparison needs to be interpreted with caution.

The study sample size is limited by feasibility. As a study to provide supportive data on retreatment options expeditiously in a difficult-to-treat population, the study sample size is small. Limitations inherent in most early phase studies apply. Safety and tolerability evaluations of each treatment regimen, as well as the virologic response, will inform the acceptability of each treatment regimen as a viable strategy for retreatment. Virologic outcome will be evaluated using SVR12 as the primary endpoint.

The primary analysis will be conducted as modified intent-to-treat, and all participants who meet the eligibility criteria and start study treatment will be included. The standard definition of SVR12 that is in use across the ACTG studies and, to our knowledge, the industry-sponsored studies will be used, where loss to follow-up or otherwise not evaluable for SVR12 is construed as not meeting the SVR12 response.

A5348 FINAL Version 1.0 09/29/15

The study regimens have different treatment durations and, while the post-treatment follow-up time is the same for both study arms, the study durations are different in Arms A and B. Assessment of reasons for not achieving SVR12 is an important part of SVR12 and SVR24 analyses in this study, including loss to follow-up. Differential loss to follow-up in the two study arms may suggest the benefit of the shorter duration in the 12-week regimen or drawback of RBV intolerance. Either way, the SVR endpoints would capture the outcome of the regimen.

- 9.2 Outcome Measures
  - 9.2.1 Primary Outcome Measures
    - 9.2.1.1 SVR12 defined as HCV RNA < lower limit of quantification (LLOQ) (either target detected [TD] or target not detected [TND]) at 12 weeks after treatment discontinuation. The sample within the week R+12 (post-treatment) visit window, as defined in section 6.0, which is closest to the targeted time will be used. If there is no HCV RNA sample within this window, then the participant will be considered SVR12 failure, unless there are preceding and subsequent HCV RNA measurements that are both <LLOQ (either TD or TND).

    - 9.2.1.2 Occurrence of Grade 3 or higher AE (diagnosis, sign, symptom, or laboratory abnormality), SAE according to ICH criteria, or AE reported as the reason for permanent discontinuation of study treatment, during study treatment and up to 30 days after study treatment discontinuation. (Event that is ongoing at the same grade from prior to study treatment initiation will be excluded.)
  - 9.2.2 Secondary Outcome Measures
    - 9.2.2.1 Renal toxicity: (a) ≥ Grade 2 creatinine clearance after study entry, or
       (b) new proteinuria and/or glucosuria, defined as ≥ 1+ or an increase ≥ 1+ from baseline.
    - 9.2.2.2 SVR4 defined as HCV RNA < LLOQ (either TD or TND) at 4 weeks after treatment discontinuation. The measurement within the week R+4 visit window that is closest to the targeted time will be used. If there is no HCV RNA sample within this window, then the participant will be considered SVR4 failure, unless there are preceding and subsequent HCV RNA measurements that are <LLOQ (either TD or TND).

- 9.2.2.3 SVR24 defined as HCV RNA < LLOQ (either TD or TND) at 24 weeks after treatment discontinuation. Sample after 20 weeks after treatment discontinuation that is closest to the targeted time, not followed by any result ≥LLOQ, will be used.
- 9.2.2.4 HCV RNA <LLOQ (either TD or TND) at post-entry scheduled visits, using the visit windows as defined in section 6.
- 9.2.2.5 HIV-1 RNA > 50 copies/mL at all scheduled visits, using the visit windows as defined in section 6.
- 9.2.2.6 Change in CD4+ cell count from study entry at subsequent scheduled visits, using the visit windows as defined in section 6.
- 9.2.3 Exploratory Outcome Measures
  - 9.2.3.1 HCV resistance mutation at study entry. The set of mutations to be considered will be defined prior to analysis based on the latest information.
  - 9.2.3.2 Development of resistance mutation in SVR12 failures.
  - 9.2.3.3 Tenofovir area under the curve (AUC) at baseline (prior to study treatment initiation) and at week 4.
  - 9.2.3.4 SOF and LDV metabolite concentrations.
- 9.3 Randomization and Stratification

The study is randomized to Arm A and Arm B and stratified by the cirrhosis status. Initially, 15 slots will be reserved for participants taking a PI/r and tenofovir regimen across the two study arms. This will be lifted 3 months after the study is open to accrual, so that the accrual progress is not constrained by the PK objective on tenofovir.

The first 15 participants whose ARV regimen contains HIV PI/r plus tenofovir who enroll to the study must be willing to participate in PK sampling (pre-dose, hour 1 and hour 4) at weeks 0 and 4. After 15 such participants have contributed PK samples, participation in the tenofovir PK sampling is optional. Study accrual may conclude with fewer than 15 participants whose ARV regimen contains HIV PI/r plus tenofovir, since the reservation of 15 slots will be lifted 3 months after the study is open to accrual. There is no minimum or maximum for such participants.

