# 1.3 Secondary Objectives

- 1.3.1 To assess the impact of LDV/SOF and ritonavir-boosted HIV protease inhibitor (PI/r) coadministration on the pharmacokinetics (PK) of tenofovir (TFV).
- 1.3.2 To assess the impact of LDV/SOF and HIV PI/r coadministration on any associated clinical events attributed to elevated tenofovir levels, including renal toxicity (defined as the development of ≥ Grade 2 renal dysfunction or development of new or worsened proteinuria or glucosuria).
- 1.3.3 To assess the proportion of participants who attain SVR4 (i.e., SVR 4 weeks after stopping HCV antiviral therapy) and SVR24 (i.e., SVR 24 weeks after stopping HCV antiviral therapy) in each study arm.
- 1.3.4 To evaluate baseline predictors of SVR12, including cirrhosis, prior treatment response (relapse, partial response, null responder), HCV genotype (GT)-1a vs. 1b, race, and IL-28B status.
- 1.3.5 To evaluate the association between LDV/SOF adherence and SVR12 in both arms.
- 1.3.6 To evaluate the impact of baseline HCV resistance mutations on the SVR12 attained with retreatment with LDV/SOF (+/- RBV).
- 1.3.7 To evaluate emergence of HCV resistance mutations in participants who fail to attain SVR12 with retreatment with LDV/SOF (+/- RBV).

- 1.3.8 To evaluate kinetics of HCV RNA during treatment (weeks 1, 2, 4, 8, 12, and in Arm B, weeks 16, 20, and 24) and 4, 12, and 24 weeks after treatment discontinuation.
- 1.3.9 To assess the influence of LDV/SOF based retreatment on HIV-specific parameters, including maintenance of HIV-1 RNA < 50 copies/mL for participants on antiretrovirals and CD4+ cell count during treatment.
- 1.3.10 To evaluate differences in SVR12 among participants receiving specific antiretroviral (ARV) therapy regimens compared to those taking no ARV on SVR12.
- 1.3.11 To compare the SVR12 proportions, safety, and tolerability in the two arms.

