4.2.1 Adverse Events and Protocol-Required Laboratory Tests

- a) Descriptive tables summarizing the adverse events and the number of participants experiencing the events will be provided by grade and by the site report on relationship to study treatment.
- b) Summary table of all diagnoses reported.
- c) Listing of participants with renal toxicity events (defined as Grade ≥ 2 creatinine clearance post-entry or new proteinuria or glucosuria, an increase from entry glucosuria or proteinuria by $\geq 1+$).
 - baseline characteristics: age, sex, race/ethnicity, ART regimen, study treatment, cirrhosis status
 - all available results on: urinalysis protein and protein, creatinine clearance (CrCl), spot protein and creatinine (and protein/creatinine ratio)
 - study treatment modifications
 - study treatment adherence
 - ARV modifications

Notes:

1. The protocol requires grading of events according to The Division of AIDS Table for Grading the Severity of Adult and Pediatric Adverse Events, Version 2.0, November 2014, which is available on the RCC website: <http://rsc.tech-res.com/safetyandpharmacovigilance/gradingtables.aspx>
2. The protocol requires the collection of signs and symptoms, diagnoses, laboratory events that
 - a. are Grade ≥ 3 post-entry
 - b. that led to a change in treatment (excluding indications for RBV dose modification) regardless of grade, or
 - c. that met ICH, EAE or SAE guidelines regardless of grade.

In addition, all creatinine, creatinine clearance (CrCl) and urinalysis results are required. Urine spot protein and creatinine are repeated in participants who develop new proteinuria or glucosuria, an increase from entry glucosuria or proteinuria by $\geq 1+$, or who develop an increase in creatinine of 0.4 from entry or CrCl < 50 , until resolution.

3. Summary tables are based on events reported on the following forms: EVW0314, EVW0315, F2860 (Hematology), F2861 (Chemistry), LBW0144 (Creatinine Clearance) and will not explicitly include events reported on EAEs to DAIDS. Before the database is finalized, the data manager will ensure that all EAE events deemed 'reportable' and included in the SDMC AR001AES table are reflected on the study CRFs.
 4. Events with date of onset or specimen date prior to the first study treatment dose will be excluded.
 5. Deaths will be described separately and not included in the safety summary tables.

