- ✓ SDAC validation: All programs generating variables as study-specific will be validated (e.g. variable to indicate participants who experienced a renal toxicity event). User-specific inputs in standard programs will also be validated.

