4.3.2 Safety

Purpose: To address the primary safety objective.

- a) Number of participants meeting the criteria noted below. The worst graded event per person over time will be used.
- b) Summaries on all reported adverse events and laboratory events and listings described in Section 4.2.1 provide supplemental information on safety.

Notes on the primary safety endpoint:

1. Occurrence of Grade ≥ 3 or higher adverse event (diagnosis, sign, symptom or laboratory event), SAE according to ICH criteria, or AE reported as the reason for permanent discontinuation of study treatment during study treatment and up to 30 days after study treatment discontinuation.
 2. Event that is ongoing at the same grade from prior to study treatment initiation will be excluded.
-
- ✓ SDAC Validation: The program deriving the indicator variable on meeting the safety endpoint criteria as described above will be validated.
 - ✓ Data sources for the primary safety endpoint: EVW0314, EVW0315, F2860 (Hematology), F2861 (Chemistry), HXW0148 (Signs and Symptoms History), LBW0144 (Creatinine Clearance), STATUS (data table on key patient characteristics and date variables including date of last dose of study treatment), CMW0029 (concomitant medication CRF table to censor data at initiation of alternate HCV treatment in case any participants erroneously remained on study when alternate HCV treatment was initiated).

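### The creatinine clearance limb of renal toxicity has no entry comparison, so a value already at Grade 2 or higher at entry and unchanged could be flagged as an event

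*Protocol*

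**What the plan says.** Protocol 9.2.2.1 gives renal toxicity two limbs. Limb (a) is "≥ Grade 2 creatinine clearance after study entry". Limb (b) is "new proteinuria and/or glucosuria, defined as ≥ 1+ or an increase ≥ 1+ from baseline". SAP 4.2.1c carries the outcome forward as "Listing of participants with renal toxicity events (defined as Grade ≥ 2 creatinine clearance post-entry or new proteinuria or glucosuria", followed by a rise in either urine measure from entry. The CrCl part again has no entry comparison.

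The outcome serves secondary objective 1.3.2, which defines renal toxicity as "development of ≥ Grade 2 renal dysfunction or development of new or worsened proteinuria or glucosuria". SAP 2.5.2, objective 2, says the same. The letter of amendment adds TDF to the exposure named in 1.3.2 and leaves the definition of renal toxicity as it was.

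For the primary safety outcome, protocol 9.2.1.2 and SAP 4.3.2 note 2 add a rule: "Event that is ongoing at the same grade from prior to study treatment initiation will be excluded". Neither 9.2.2.1 nor SAP 4.2.1 has it. The nearest rule in SAP 4.2.1 is note 4: "Events with date of onset or specimen date prior to the first study treatment dose will be excluded".

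The definition drives a derived item. SAP 4.2.1 requires validation of a "variable to indicate participants who experienced a renal toxicity event". For each flagged participant the listing gives "baseline characteristics: age, sex, race/ethnicity, ART regimen, study treatment, cirrhosis status" and all available CrCl results.

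**The concern.** Limb (a) describes a state: a value at Grade 2 or higher seen after entry. The objective describes a change: dysfunction that develops. The two differ for a participant who enters at Grade 2 or higher and stays there. That participant has developed nothing, yet meets limb (a) as worded.

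A programmer working from SAP 4.2.1c would set the indicator to yes for this participant, and validation against the same text would confirm it. Under SAP Version 2.0 the final report consists mainly of listings of endpoints, so who enters the renal listing is in effect the renal result.

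**Working it through.** The plan states no renal event rate, sample size or precision, so there is no figure to reproduce. The check is textual, followed by the conditions that decide the size.

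**Step 1. Which rules refer to entry**

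| Place | What it governs | Tied to entry or baseline? |
|---|---|---|
| Protocol 1.3.2; SAP 2.5.2 objective 2 | Objective | Yes, dysfunction must develop |
| Protocol 9.2.2.1(a) | Outcome, CrCl limb | No |
| Protocol 9.2.2.1(b) | Outcome, urine limb | Yes |
| SAP 4.2.1c | Renal listing and indicator | CrCl no, urine yes |
| Protocol 9.2.1.2; SAP 4.3.2 note 2 | Primary safety outcome | Yes, unchanged grade excluded |

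Protocol 6.3.7 (team notification) and 7.1.3.1 (work-up) also refer to new or worsened values or to change from entry. They are operational rules, not outcome definitions, and carry less weight.

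**Step 2. Do the date rules close the gap?** Take a participant at Grade 2 at entry and at Grade 2, unchanged, at week 4.

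- SAP 2.8 limits summaries of adverse events, diagnoses and opportunistic infections to onset on or after treatment start. It does not name serial laboratory values or say how onset is assigned to them.
- SAP 4.2.1 note 4 excludes by onset date or specimen date. The week 4 specimen date is after the first dose. If onset is taken as the first abnormal value, the record goes out; if the specimen date is used, it stays in.

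The text supports either result, so the date rules do not clearly exclude the record.

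**Step 3. The two rules compared**

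| Entry | After first dose | As worded | New or worse than entry |
|---|---|---|---|
| Below Grade 2 | Below Grade 2 | no event | no event |
| Below Grade 2 | Grade 2 or higher | event | event |
| Grade 2 or higher | same grade | event | no event |
| Grade 2 or higher | higher grade | event | event |

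They differ only in the third row.

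**Step 4. Can the third row occur?** Protocol 4.1.10 requires CrCl of at least 60 mL/min within 42 days before entry. The grades come from DAIDS table Version 2.0, whose CrCl limits are not printed in either document. Call the Grade 2 limit L and assume it is an absolute value.

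- L at or below 60: the floor keeps nearly everyone out of the third row. The remaining route is a fall between screening and entry. For an assumed man of 50 years and 70 kg, the protocol's Cockcroft-Gault formula gives (140 − 50) × 70 / 72 = 87.5, divided by creatinine. At 1.4 mg/dL this is 87.5 / 1.4 = 62.5 mL/min (eligible); at 1.5 mg/dL it is 87.5 / 1.5 = 58.3 mL/min (below 60 at entry).
- L above 60: every stable entrant between 60 and L is in the third row. An assumed man of 55 years and 75 kg with creatinine 1.1 mg/dL has (140 − 55) × 75 / (72 × 1.1) = 6375 / 79.2 = 80.5 mL/min. If L were 90 he would be flagged with no change; if L were 70 he would not.

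If the grade itself depends on change from baseline, the effect is smaller in either case.

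**The case against.** The best reply is that the documents can be read consistently. The objective says what renal toxicity means, the outcome carries that label, protocol 9.6 lists a time of failure (which presupposes an onset), and SAP 2.8 restricts adverse events to onset after treatment start. On that reading a stable abnormality has a pre-dose onset and drops out. This is a fair account of what was probably intended. It does not settle what will be programmed, because no rule assigns onset to a serial laboratory value and note 4 also works by specimen date.

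Second, the listing shows all available CrCl results for each flagged participant, so a careful reader could see that a value had not moved. That stands and limits the harm. The indicator would still disagree with the objective, and the listing's baseline columns do not include entry CrCl or its grade.

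Third, no renal proportion, interval or test is planned, and broad capture in a small nephrotoxicity listing is defensible. That also stands; the fix therefore keeps declines visible and does not discard them.

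A reader might go further and infer that a known share of the seven enrolled participants would be wrongly flagged. The documents do not support that. The Grade 2 limit is not printed and entry CrCl values are not given. Seven is everyone enrolled, on any ARV regimen or none, whereas objective 1.3.2 concerns those on a boosted protease inhibitor with TDF, whose number is not stated.

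**Conclusion.** The inconsistency is real and lies in a stated rule. Limb (a) and SAP 4.2.1c count a state where the objective asks for a change, and no other rule clearly repairs this. Programmed literally, the validated indicator could mark a stable participant as a renal toxicity event.

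The size cannot be fixed from the documents, and no percentage should be attached. With an absolute Grade 2 limit it ranges from near nil (limit at or below 60 mL/min) to every stable entrant between 60 and the limit (limit above 60). It is less if grading uses change from baseline.

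The outcome is secondary and descriptive. It would be wrong to infer that the primary safety outcome is affected, since that outcome has its own same-grade exclusion. The point is worth correcting before the indicator is programmed, and its weight should not be put higher than that.

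**What to change.** In protocol 9.2.2.1(a) and SAP 4.2.1c, count Grade 2 or higher CrCl after treatment start only when the grade is new or worse than the entry grade. Use the entry value as SAP 2.8 already defines it, and extend the rule in SAP 4.3.2 note 2 to the renal outcome. If the protocol is not to be amended, changing the SAP alone is enough.

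In the SAP 4.2.1c listing, show entry CrCl and its grade among the baseline columns. List separately any participant who enters at Grade 2 or higher and declines within that grade.

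The cost is a change of wording in one or two places, two listing columns and a short extra listing. No new tests are needed, because protocol 6.3.7 already has all entry laboratory values and all post-entry grades of CrCl recorded. The one downside is that declines within a grade already present at entry leave the event count; the separate listing keeps them in view. The change concerns only how the outcome is derived, not any clinical management rule.
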